Blood samples will be obtained from all subjects (cases and controls) at the screening visit and monthly throughout the 16 weeks of the study duration (weeks 1, 5, 9, 13, 17, 21), and weekly after the 16-week intervention for 4 weeks (week 22 - 25). Blood samples will be sent to Quest Diagnostics for determining the serum 25(OH)D levels. The study design summarized in Figure 1 and Table 2

If a subject needs to end his/her regiment early they will be able to do so, with no change to the study procedure. We will require a final blood sample collection from the study subject prior to his/her removal.

We anticipate the entire study will take 12 months to complete 16-week treatment for case group. As discussed earlier the study subject's involvement will last 26 weeks from screening to completion include one week for screening, 5 weeks for titration, 16 weeks for treatment and 4 weeks of post-treatment serum 25(OH)D monitoring.

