# 12 Statistical Plan

The endpoint is the difference in vitamin D insufficiency/sufficiency prevalence between the treatment and the control group use at 16 weeks of follow-up. The subject will have at least one serum 25(OH)D

evaluation within 16 weeks, and at least one phototherapy session in the 16 weeks follow up. The protocol includes a sample size calculation, which allowed for a loss to follow-up of 15%.

Statistical analysis will be performed using SPSS Statistics, version 25 (IBM Corporation). Age, sex, BMI, and Fitzpatrick skin type will be matched in two study groups. Two-sided P < .05 will be considered significant. All models will be developed according to the intention-to-treat principle. A supportive analysis will also be conducted on the per-protocol (PP) population.

The biological and clinical characteristics at enrolment will be presented, and all variables for the participants in the treatment and control groups will be compared at each follow-up using Fisher's exact test for categorical variables and a Mann–Whitney *U* test for continuous variables. For intergroup differences, 95% CIs will be also calculated. The endpoint, the proportion of subjects converting from vitamin D deficiency/insufficiency to vitamin D insufficiency/sufficiency at 16 weeks will be compared between groups using Fisher's exact test and logistic regression adjusting for skin types. Secondary analysis will be involved a comparison of changing in serum levels of 25(OH)D between groups using a Mann–Whitney *U* test and linear regression adjusting for skin types. A linear mixed model will be used to examine the relationship between phototherapy and serum 25(OH)D3 at different time points, adjusting for the baseline values and correlation of outcomes within individuals and season.

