## 12.2 Sample Size Determination

The endpoint of this study is to compare the improvement of vitamin D status between treatment group and the controls. A previous study by Chandra et al. demonstrated the increase in the mean serum 25(OH)D in subjects with malabsorption syndrome receiving UV therapy from 21± 3 ng/mL to 27±4 ng/mL after 8 weeks (13). We would expect that to increase the serum 25(OH)D level by 10 ng/mL (SD=5ng/ml), after 16 weeks based on a previous study (13) as well as an earlier pilot study that was completed by Solius.

The endpoint is to improve vitamin D status in the treatment group compared to sham controls. We expect that the serum levels of 25(OH)D will increase more than 10 ng/ml (SD=5ng/ml) after 16 weeks of intervention in the treatment group compared to controls. Subjects converted from vitamin D deficient/insufficient to insufficient/sufficient is considered a minimum clinical important difference (MCID). We expect at least 70% of vitamin D deficient/insufficient subjects in the treatment group to convert to insufficient/ sufficient. Also, because of seasonal variations and other confounders, we expect maximum 30% of subject convert to insufficient/sufficient in sham control. With the desired power of 80% and significance level ( $\alpha$ ) of 0.01, the sample size in each group is 35.

Approximately 100 adult subjects with 5 skin types group (I, II, III, IV and V/VI) will be enrolled for vitamin D deficiency/ insufficiency screening. We expect that at least 80% of the population in the

Boston area has a level of 25(OH)D below 30 ng/ml. Thus, we will enroll 100 subjects with different skin types to enroll 80 vitamin D deficient or insufficient subjects in this study. We plan to match treatment and control group for age, sex, BMI and skin type by stratified random sampling (40 subjects in each group). In our experience, the rate of screen failure and subject dropout is 10-15%. Then, we expect to have at least 35 subjects per each group.

Parameters	Value
Conversion of the subjects from vitamin D deficient to vitamin D	70%
insufficient/sufficient or vitamin D insufficient to vitamin D sufficient in the	
treatment group after 16 weeks (P1)	
Conversion of the subjects from vitamin D deficient to vitamin D	30%
insufficient/sufficient or vitamin D insufficient to vitamin D sufficient in the control	
group after 16 weeks (P2)	
Significant level	0.01
Power	80%

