$$\begin{split} N_1 &= \left\{ z_{1-\alpha/2} * \sqrt{\bar{p} * \bar{q} * (1 + \frac{1}{k})} + z_{1-\beta} * \sqrt{p_1 * q_1} + (\frac{p_2 * q_2}{k}) \right\}^2 / \Delta^2 \\ q_1 &= 1 - p_1 \\ q_2 &= 1 - p_2 \\ \bar{p} &= \frac{p_1 + k p_2}{1 + K} \\ \bar{q} &= 1 - \bar{p} \\ N_1 &= \left\{ 2.58 * \sqrt{0.5 * 0.5 * (1 + \frac{1}{1})} + 0.84 * \sqrt{0.7 * 0.3 + (\frac{0.3 * 0.7}{1})} \right\}^2 / 0.4^2 \\ N_1 &= 35 \\ N_2 &= K * N_1 = 35 \\ N_2 &= K * N_1 = 35 \\ \end{split}$$

The research coordinator will be responsible for randomization and allocation. Thus, the study will be blinded to other members of the research team. We expect that the serum levels of 25(OH)D will increase by at least 10 ng/ml in the treatment group compared to the control group after 16 weeks UV exposure in a linear fashion. We will do an assessment every four weeks, expecting that there will be a minimum of 2.5 ng/ml increase in the serum 25(OH)D. We will conduct the blinded interim analyses to re-assess the planned sample size after thirty five subjects in each group have completed four weeks of

intervention by an independent statistician. The sample size adjustment will be made to ensure the appropriate power to determine the effect of UV exposure on vitamin D synthesis.

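### Does the late, loosely specified blinded sample-size re-assessment in Section 12.2 leave the trial's power unprotected?

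*Combined protocol and SAP*

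**What the plan says.** All of the relevant text on the re-assessment is in Section 12.2 (Sample Size Determination) of the combined protocol and SAP.

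- **Target.** For conversion of 70% versus 30% at 80% power, the section states a significance level of "0.01, the sample size in each group is 35". It enrols 40 per group to allow for losses: "Then, we expect to have at least 35 subjects per each group".
- **Re-assessment.** A statistician independent of the study is to run the look, planned as "blinded interim analyses to re-assess the planned sample size after thirty five subjects in each group have completed four weeks of" study treatment. Its purpose is given as: "The sample size adjustment will be made to ensure the appropriate power to determine the effect of UV exposure on vitamin D synthesis".
- **Context.** The sentence just before describes four-weekly assessments, "expecting that there will be a minimum of 2.5 ng/ml increase in the serum 25(OH)D".

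Section 12 (Statistical Plan) sets the endpoint: "the proportion of subjects converting from vitamin D deficiency/insufficiency to vitamin D insufficiency/sufficiency at 16 weeks will be compared between groups", by Fisher's exact test at two-sided 0.05. It does not mention the re-assessment.

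Section 9 (Study Procedures) gives the calendar: "We anticipate the entire study will take 12 months to complete" the treatment course, and each subject's "involvement will last 26 weeks from screening to completion". The visit table in Section 5 places intervention after five titration weeks, so four weeks of intervention end at week 9 and the 16-week endpoint falls at week 21.

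**The concern.** Three features look wrong together.

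1. **Timing.** The trigger needs 70 of the 80 planned subjects to be nine weeks in. Recruitment has probably finished by then, so any increase means reopening it, and the plan gives no time or ceiling for that.
2. **Missing rule.** The sample size rests on 16-week conversion, while the neighbouring sentence speaks of a four-week gain in serum 25(OH)D. Different choices of quantity give very different answers.
3. **Claim.** Blinded data pool the two groups and do not show the treatment difference. A look of this kind cannot assure power against a smaller effect.

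At stake would be an underpowered trial whose readers believe it was protected, and a rule chosen after data had accumulated. The trial is meant to meet a regulatory request for a statistically significant result (Section 3.2), so both would matter.

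**Working it through.** **1. The plan's own figure.** Inputs from Section 12.2: p1 = 0.70, p2 = 0.30, equal allocation, z = 2.58 and 0.84.

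N = {2.58 × √(0.5 × 0.5 × 2) + 0.84 × √(0.21 + 0.21)}² / 0.4² = 35.07, which the plan gives as 35.

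With unrounded z values the result is 35.01. The figure reproduces. At 15% loss, 40 per group leaves 34; at 12.5% it leaves 35.

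**2. When the look falls.** The accrual rate is not in the documents, so take uniform accrual of 80 subjects over W weeks. The 70th subject enters at (70/80)W = 0.875W and reaches week 9 at 0.875W + 9. Twelve months less 26 weeks of participation leaves W of about 26.

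- Trigger: 0.875 × 26 + 9 = 31.75 weeks. The last enrolment is at week 26.
- The trigger precedes the last enrolment only if 0.125W > 9, that is W > 72, which does not fit 12 months.

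So the timing point is factually right under this assumption.

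**3. What an earlier look would know.** The endpoint needs week-21 data.

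| Look (W = 26) | Subjects with week-21 data | Half-width of 95% interval for a pooled rate near 50% |
|---|---|---|
| Planned trigger, week 31.75 | 80 × (31.75 − 21)/26 = 33 | 1.96 × √(0.25/33) = 17 points |
| When enrolment closes, week 26 | 80 × (26 − 21)/26 = 15 | 1.96 × √(0.25/15) = 25 points |

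Moving the look forward loses more than half of the endpoint information. Once all 80 are enrolled, a re-assessment also cannot cut enrolment below 40 per group, so the missing lower limit has no practical effect.

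**4. How much the unnamed quantity matters.** At two-sided 0.01 and 80% power, N per group is:

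- gain of 10 ng/mL with SD 5 (Section 12.2): 2 × (5/10)² × (2.576 + 0.842)² = 5.8, so 6;
- gain of 2.5 ng/mL at four weeks: 24 if the SD is 2.5 and 94 if it is 5 (the four-week SD is an assumption);
- conversion with the 40-point difference held: 35.0 at a pooled rate of 50%, 33.5 at 40%, 29.2 at 30%.

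The spread is real. The last line also shows that this particular rule could not raise N, because the formula peaks at the planned pooled rate of 50%. But the plan does not adopt that rule.

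**5. What the main comparison has without the look.** Exact Fisher power:

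| Conversion rates | N per group | Two-sided 0.05 (Section 12) | Two-sided 0.01 (Section 12.2) |
|---|---|---|---|
| 70% vs 30% | 35 | 88% | 75% |
| 70% vs 30% | 40 | 94% | 81% |
| 65% vs 35% | 40 | 72% | 46% |

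For 65% versus 35%, the plan's formula asks for 63.4 per group at 0.01 and 42.4 at 0.05. Against 40 enrolled, most of that gap comes from the two significance levels in the plan, which is a separate matter from the look.

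**The case for a change.** The strongest case for acting is that an adaptive step without a written quantity, formula or ceiling leaves a choice to be made once data exist. Answers of 6, 35 or 94 per group could each be argued from the present text. If the true rates were 65% and 35%, the pooled rate would still be 50%; a fixed-difference rule would return 35 when about 63 are needed at 0.01, and the plan would have promised adequate power. If losses come early and reach 15%, 34 per group remain and the trigger may never be met.

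Part of this stands. The rule is unwritten, and the sentence on power claims more than any blinded look can deliver. But the consequences are limited:

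- **The discretion is blinded.** The independent statistician works without the difference between groups, so the choice of quantity cannot be steered towards a favourable result. Setting the rule down before the look is ordinary practice.
- **The 65% versus 35% case is outside the plan's premises.** Section 12.1 expects at least 70% and at most 30%. Failure to see a smaller effect is a general limit of blinded re-estimation that holds the planned difference fixed.
- **A trigger that is never met does no harm.** The trial then runs as a fixed design with 40 enrolled per group.

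The possible remedies gain little. Deleting the look removes the only sample-size safeguard and leaves the 65% versus 35% power where it is. An earlier look knows less about the endpoint. Rewording the power sentence changes no result.

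**Conclusion.** The observations are accurate, but none calls for a change to the plan. The unnamed quantity and limits are a gap that an independent statistician can fill before looking. The late trigger is a fair trade between open enrolment and endpoint information (about 33 against 15 subjects with week-21 data). The claim about assured power is loose wording with no analysis attached to it.

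The comparison of conversion at 16 weeks stays sound whether or not the look takes place: 88% exact power with 35 per group and 94% with 40, at 70% versus 30% and two-sided 0.05. The timing figures rest on uniform accrual over about 26 weeks, which the documents do not state. The power figures rest on the plan's own conversion rates and on the 0.05 level in Section 12; at the 0.01 level in Section 12.2 they are 75% and 81%.

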## 13 Ethics/Protection of Human Subjects

This study is to be conducted according to applicable US federal regulations and institutional policies (which are based in federal regulations, guidance, and ICH Good Clinical Practice guidelines).

This protocol and any amendments will be submitted to the Boston Medical Center and Boston University Medical Campus IRB, for formal approval of the study conduct. The decision of the IRB concerning the conduct of the study will be made in writing to the investigator.

All subjects for this study will be provided a consent form describing this study and providing sufficient information for subjects to make an informed decision about their participation in this study. The consent form will be submitted with the protocol for review and approval by the IRB. The consent of a subject, using the IRB-approved consent form, must be obtained before that subject is submitted to any study procedure. Consent will be documented as required by the IRB.

